12.4.1. Definition of Adverse Events

Adverse Event Definition:

- An AE is any untoward medical occurrence in a patient or clinical investigation subject, temporally associated with the use of a medicinal product, whether or not considered related to the medicinal product.
- NOTE: An AE can therefore be any unfavorable and unintended sign (including an abnormal laboratory finding), symptom, or disease (new or exacerbated) temporally associated with the use of a medicinal product.

Events meeting AE definition include:

- Any abnormal laboratory test results (hematology, clinical chemistry, or urinalysis) or other safety assessments (e.g., ECGs, radiological scans, vital signs measurements), including those that worsen from baseline, and felt to be clinically significant in the medical and scientific judgement of the investigator.
- Exacerbation of a chronic or intermittent pre-existing condition including either an increase in frequency and/or intensity of the condition.
- New conditions detected or diagnosed after study treatment administration even though it may have been present prior to the start of the study.
- Signs, symptoms, or the clinical sequelae of a suspected interaction.
- Signs, symptoms, or the clinical sequelae of a suspected overdose of either study treatment or a concomitant medication (overdose per se will not be reported as an AE/SAE unless this is an intentional overdose taken with possible suicidal/self-harming intent. This should be reported regardless of sequelae).
- "Lack of efficacy" or "failure of expected pharmacological action" per se will not be reported as an AE or SAE. However, the signs and symptoms and/or clinical sequelae resulting from lack of efficacy will be reported if they fulfil the definition of an AE or SAE.

Events NOT meeting definition of an AE include:

- Any clinically significant abnormal laboratory findings or other abnormal safety assessments which are associated with the underlying disease (influenza symptoms), unless judged by the investigator to be more severe than expected for the subject's condition.
 - Influenza symptoms: nasal symptoms (rhinorrhea, congestion), feverishness, cough, myalgia, fatigue, diarrhea, dyspnea, headache, sore throat, nausea and

vomiting.

- The disease/disorder being studied or expected progression, signs, or symptoms of the disease/disorder being studied, unless more severe than expected for the subject's condition.
- Medical or surgical procedure (e.g., endoscopy, appendectomy): the condition that leads to the procedure is an AE.
- Situations where an untoward medical occurrence did not occur (social and/or convenience admission to a hospital).
- Anticipated day-to-day fluctuations of pre-existing disease(s) or condition(s) present or detected at the start of the study that do not worsen.

12.4.2. Definition of Serious Adverse Events

If an event is not an AE per definition above, then it cannot be an SAE even if serious conditions are met (e.g., hospitalization for signs/symptoms of the disease under study, death due to progression of disease, etc).

Serious Adverse Event (SAE) is defined as any untoward medical occurrence that, at any dose:

a. Results in death

b. Is life-threatening

NOTE:

The term 'life-threatening' in the definition of 'serious' refers to an event in which the subject was at risk of death at the time of the event. It does not refer to an event, which hypothetically might have caused death, if it were more severe.

c. Requires hospitalization or prolongation of existing hospitalization

NOTE:

- In general, hospitalization signifies that the subject has been detained (usually involving at least an overnight stay) at the hospital or emergency ward for observation and/or treatment that would not have been appropriate in the physician's office or out-patient setting. Complications that occur during hospitalization are AEs. If a complication prolongs hospitalization or fulfills any other serious criteria, the event is serious. When in doubt as to whether "hospitalization" occurred or was necessary, the AE should be considered serious.
- Hospitalization for elective treatment of a pre-existing condition that did not worsen from baseline is not considered an AE.

d. Results in disability/incapacity

NOTE:

- The term disability means a substantial disruption of a person's ability to conduct normal life functions.
- This definition is not intended to include experiences of relatively minor medical significance such as uncomplicated headache, nausea, vomiting, diarrhea, influenza, and accidental trauma (e.g. sprained ankle) which may interfere or prevent everyday life functions but do not constitute a substantial disruption

e. Is a congenital anomaly/birth defect**f. Other situations:**

- Medical or scientific judgment should be exercised in deciding whether reporting is appropriate in other situations, such as important medical events that may not be immediately life-threatening or result in death or hospitalization but may jeopardize the subject or may require medical or surgical intervention to prevent one of the other outcomes listed in the above definition. These should also be considered serious.
- Examples of such events are invasive or malignant cancers, intensive treatment in an emergency room or at home for allergic bronchospasm, blood dyscrasias or convulsions that do not result in hospitalization, or development of drug dependency or drug abuse

g. Is associated with liver injury and impaired liver function defined as:

- ALT \geq 5xULN and total bilirubin* \geq 2xULN (>35% direct), **or**
- ALT > 10xULN.

* Serum bilirubin fractionation should be performed if testing is available; if unavailable, measure urinary bilirubin via dipstick. If fractionation is unavailable and ALT \geq 3xULN and total bilirubin \geq 2xULN, then the event is still to be reported as an SAE.

** INR testing not required per protocol and the threshold value does not apply to subjects receiving anticoagulants. If INR measurement is obtained, the value is to be recorded on the SAE form.

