4.6.1. Risk Assessment

Potential Risk of Clinical Significance	Summary of Data/Rationale for Risk	Mitigation Strategy
Investigational Product (IP) GSK 1325756		
Reduction in Peripheral Blood Neutrophils	Peripheral neutropenia has been reported in clinical trials of other irreversible CXCR2 antagonists MK-7123 [Seiberling, 2013], SCH527123 [Nair, 2012] and AZD5069 [Kirsten, 2015]. Reduction in peripheral blood neutrophils may occur after a single dose. Peripheral blood neutrophils return to baseline approximately 24 to 48 hours after withdrawal of the CXCR2 antagonist.	Refer to the Time and Events Table (Section 7.1) for neutrophil monitoring. Peripheral blood neutrophil count of $<1.0 \times \text{Gi/L}$ is an exclusion criterion. Also, any subject that has a peripheral blood neutrophil count of $<0.5 \times \text{Gi/L}$ at two successive measures, will be withdrawn from IP and monitored until the neutrophil count returns to pre-dose levels.
Infection Risk	
Neutrophils are an important component of host defense and innate immunity. Inhibition of neutrophil migration and activation could impact host defense and innate immunity and increase the risk of bacterial super- infection or worsening influenza virus-mediated disease..
 
Nonclinical studies in mice and ferrets with two CXCR2 antagonists in the same chemical class as DNX have not shown an increase in influenza viral load [GSK Document Number YM2010/00163/07] Secondary bacterial infections after viral infection have not been directly evaluated in nonclinical studies.
	
The site will monitor adverse events, complications of influenza (such as pneumonias [bacterial, ventilator, hospitalized and community], pneumothorax, pleural effusion, ARDS, myositis, encephalitis, myocarditis, bacterial bronchitis, otitis media, sepsis, sinusitis, bacteremia) and frequency of new associated antibiotic use and clinical symptoms of subjects during treatment and post-treatment. Also chest x-ray will be obtained at baseline for clinical comparison throughout treatment.
 
Subjects will be discontinued from IP if develop significant worsening of symptoms or strong

Potential Risk of Clinical Significance	Summary of Data/Rationale for Risk	Mitigation Strategy
		suspicion or confirmation of progressive secondary bacterial infections or require antibiotics. In addition, the study has halting criteria that are part of the IDMC review.

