7.4.1.4. Cardiovascular and Death Events

For any cardiovascular events detailed in [Appendix 4](#) and all deaths, whether or not they are considered SAEs, specific Cardiovascular (CV) and Death sections of the CRF will be required to be completed. These sections include questions regarding cardiovascular (including sudden cardiac death) and non-cardiovascular death.

The CV eCRFs are presented as queries in response to reporting of certain CV Medical Dictionary for Regulatory Activities (MedDRA) terms. The CV information should be recorded in the specific cardiovascular section of the eCRF within one week of receipt of a CV Event data query prompting its completion.

The Death CRF is provided immediately after the occurrence or outcome of death is reported. Initial and follow-up reports regarding death must be completed within one week of when the death is reported.

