8. SECONDARY STATISTICAL ANALYSES

8.1. Efficacy Analyses

8.1.1. Overview of Planned Efficacy Analyses

The secondary efficacy analyses will be based on the IPP population, unless otherwise specified. Table 5 provides an overview of the planned efficacy analyses, with full details of data displays being presented in Appendix 13: List of Data Displays. Given the small number of subjects, only time to respiratory response will be summarized. Data relevant to other secondary endpoints will be listed including vital signs, ventilation status, hospital discharge, hospital re-admission, and ICU stay.

Table 5 Overview of Planned Secondary Efficacy Analyses

Endpoint	Stats Analysis			Analysis Summary		ummary Individua	
	Т	F	L	T	F	F	L
	Absolute						
Time to Respiratory Response (TTRR)				Y [1]			

^[1] Proportion of clinical response and Kaplan Meier estimates for the median of TTCR for each treatment group and the median difference and 95% CI between two comparisons: each DNX arm and OSV will be provided

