11.13.18. ICH Listings

ICH : Li	ICH : Listings						
No.	Population	IDSL / TST ID / Example Shell	Title	Programming Notes			
Subjec	Disposition						
1.	All Subjects Screened	ES7	Listing of Screen Reasons for Screen Failure				
2.	ITT-E	ES2	Listing of Reasons for Study Withdrawal				
3.	ITT-E	SD2	Listing of Reasons for Study Treatment Discontinuation				
4.	ITT-E	BL1	Listing of Subjects for Whom the Treatment Blind was Broken				
5.	ITT-E	TA1	Listing of Planned and Actual Treatments				
Protoco	ol Deviations						
6.	ITT-E	DV2	Listing of Important Protocol Deviations				
7.	ITT-E	IE3	Listing of Subjects with Inclusion/Exclusion Criteria Deviations				
Popula	tions Analysed						
8.	All Subjects Screened	SA3a	Listing of Subjects Excluded from Any Population				
Demog	Demographic and Baseline Characteristics						
9.	ITT-E	DM2	Listing of Demographic Characteristics				
10.	ITT-E	DM9	Listing of Race				

ICH : Li	ICH : Listings						
No.	Population	IDSL / TST ID / Example Shell	Title	Programming Notes			
11.	ITT-E	CM2	Listing of Concomitant Medications	Add column to indicate 'complications of influenza'			
12.	ITT-E	MH2	Listing of Past and Current Medical Conditions				
13.	ITT-E	MH2	Listing of Subjects with Renal Impairment	Renal impairment is based on Creatinine Clearance Criteria Any time during study including baseline and post baseline			
14.	IIT-E	CM2	Listing of Subjects with Prior Oseltamivir Exposure				
Exposu	re and Treatme	ent Compliance					
15.	Safety	EX3	Listing of Exposure Data				
Advers	e Events						
16.	Safety	AE8	Listing of All Adverse Events	Add asterisk for subjects with baseline renal impairment			
17.	Safety	AE2	Listing of Relationship Between Adverse Event System Organ Classes, Preferred Terms, and Verbatim Text				
18.	Safety	AE8	Listing of Adverse Events of Special Interest				
Serious	and Other Sig	nificant Adverse l	Events				
19.	Safety	AE8	Listing of Fatal Adverse Events				
20.	Safety	AE8	Listing of Non-Fatal Serious Adverse Events				
21.	Safety	SAFE L1	Listing of Reasons for Considering as a Serious Adverse Event	Use study 201682 as a reference			

ICH : Li	ICH : Listings						
No.	Population	IDSL / TST ID / Example Shell	Title	Programming Notes			
22.	Safety	AE8	Listing of Adverse Events Leading to Withdrawal from Study				
23.	Safety	AE8	Listing of Adverse Events Leading to Permanent Discontinuation of Study Treatment`				
24.	Safety	MH2	Listing of Subjects with Liver Stopping Events				
All Lab	oratory						

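### The SAP's death displays depend on adverse-event status, so a death judged to be expected influenza progression can fall outside every death-specific display; an all-cause death count and listing are needed

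*Protocol*

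**What the plan says.** **Definitions (Protocol, Appendix 4).** Section 12.4.1 lists among events that are not AEs "expected progression, signs, or symptoms of the disease/disorder being studied, unless more severe than expected" for that subject. Section 12.4.2 then says: "If an event is not an AE per definition above, then it cannot be an SAE even if serious conditions are met". Its examples are "hospitalization for signs/symptoms of the disease under study, death due to progression of disease, etc". The same section also treats complications arising in hospital as AEs, and as serious if they meet a seriousness criterion.

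**Collection (Protocol 7.4.1.4 and 7.4.1.5).** The Death section of the CRF is required for "all deaths, whether or not they are considered SAEs". Disease-related complications, including pneumonias, ARDS, sepsis and bacteremia, are AEs of special interest with their own CRF page.

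**Named risk (Protocol 4.6.1).** The infection-risk row gives bacterial super-infection and "worsening influenza virus-mediated disease" as possible consequences of inhibiting neutrophils.

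**Reporting (SAP).** Table 6 in section 8.2.1 plans a listing of fatal SAEs. In section 11.13.18, listing 19 is the "Listing of Fatal Adverse Events". On secondary efficacy, section 8.1.1 says: "Given the small number of subjects, only time to respiratory response will be summarized". Section 7.1.2 gives TTCR a value of 99 days when death precedes response. Section 11.6.4 does not count a death after response as a failure.

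**The concern.** In patients hospitalised with influenza, the investigator decides whether a fatal course was expected progression. If it was, the death is not an AE and so cannot enter a display of fatal AEs. Worsening influenza is also a harm the protocol says this drug might cause, so the excluded category overlaps with one the safety report should be able to show. A comparison of fatal events between arms then rests on a judgement about cause and expectedness, whereas a count of deaths from any cause needs neither. What is at stake is whether the final report accounts for every death by arm.

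**Working it through.** No arithmetic underlies this point beyond the one fraction in step 5. The check compares the protocol's definitions with the SAP's display list.

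1. **Is an expected-progression death an AE or SAE?** No, by Protocol 12.4.1 and 12.4.2 read together. Progression worse than expected remains an AE.

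2. **Is it recorded?** Yes. Protocol 7.4.1.4 requires the Death CRF for every death.

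3. **Does a safety display use that record?** Going by titles in SAP 11.13, none of the 19 safety tables, 2 safety figures or 54 listings is an all-cause death display. One listing (no. 19) is specific to deaths, and it covers fatal AEs only. Protocol 9.4.2 names no death summary either.

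4. **Do the efficacy outputs fill the gap?** The ordinal scale has a death category, but SAP 8.1.1 no longer summarises it. For TTCR there are four cases for a death judged to be expected progression:

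| | Death before response | Death after response |
|---|---|---|
| In the IPP | Not in listing 19; TTCR = 99 days | Not in listing 19; TTCR counts a response |
| Outside the IPP | Not in listing 19; not in the TTCR analysis | Not in listing 19; not in the TTCR analysis |

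In the first case the death can be recognised, because 99 days exceeds the 45 days of follow-up. In the other three it has neither a fatal-event entry nor a TTCR mark. The after-response column matters because discharge for clinical improvement is itself a response, while follow-up continues to Day 45. A subject discharged as improved who later dies of influenza counts as a TTCR success.

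5. **Size.** The documents give no mortality figure. The SAP reports 10 subjects enrolled, so one such death would be 1/10 = 10% of the trial.

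6. **Are the protocol's own rules consistent?** Not for fatal cases. Section 7.4.1.5 makes serious disease-related complications AESIs, and 12.4.2 makes hospital complications AEs. Yet 12.4.2 also exempts death from progression. No section says which rule applies when such a complication is fatal and the investigator regards it as expected progression.

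**The case against.** The strongest reply is that few deaths would escape. Progression worse than expected stays an AE. Pneumonia, ARDS, sepsis and bacteremia are AESIs with a Safety-population table (3.8) and a listing (18), so a death through one of them should reach listing 19. This stands, and it narrows the point considerably. It does not close it: whether a course was expected is a judgement, it protects least in critically ill subjects, and the rules for a fatal AESI conflict as shown.

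Four stronger readings are tempting, and the documents do not support them.

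- **That such a death would appear nowhere.** Protocol 5.4 counts anyone who misses the Day 45 visit as prematurely withdrawn, so the subject is a non-completer in the disposition table (1.1) and the withdrawal listing (2). SAP 2.1 also promises that all data will be listed, and the mock shells are in a separate document, so a death line in one of them cannot be ruled out. But death is not among the withdrawal reasons in Protocol 5.4, and a general promise is not a specified all-cause display.
- **That the drug's main harm is hidden.** Protocol 4.6.1 names worsening influenza alongside bacterial super-infection and does not rank them.
- **That the IDMC would not see these deaths.** Protocol 10.8.1 gives it all available safety data and has it compare disease progress between arms.
- **That the gap can be scaled to the planned 300 subjects.** This display list was written after termination at 10. For the full trial, Protocol 9.4.1.2 planned to summarise the ordinal scale, which includes death.

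**Conclusion.** The point holds as a reporting gap. A death attributed to expected influenza progression that occurs after response or outside the IPP is in no death-specific display, although the Death CRF holds the record. Whether a death appears among fatal events therefore depends on a judgement that overlaps with a named potential risk of the drug.

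The practical size is small and may be zero. Under Protocol 4.1.1 the first approximately 30 subjects were to be less severely ill with normal renal function, so the 10 enrolled may include no deaths. If there were one of this kind, 10% of the trial would be missing from the fatal-event display. The conclusion rests on the display titles and the AE definitions as written; the mock shells and the IDMC charter are not available. The remedy uses data already collected and should be adopted.

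**What to change.** 1. In the SAP, add a table of all-cause deaths by arm and a listing of every death, on the Safety population through Day 45, taken from the Death CRF. Include each death regardless of AE status, IPP membership or prior clinical response. The listing should show study day, recorded cause, whether the event was also an AE, SAE or AESI, and whether response came first.

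2. Reconcile Protocol 7.4.1.5, 12.4.1 and 12.4.2 on how a fatal disease-related event is classified. With enrolment ended, a note in the SAP or the report stating the rule applied would serve.

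The cost is one small table, one listing and a short clarification, with no new data collection.

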12.4.3. Definition of Cardiovascular Events**Cardiovascular Events (CV) Definition:**

Investigators will be required to fill out the specific CV event page of the CRF for the following AEs and SAEs:

- Myocardial infarction/unstable angina
- Congestive heart failure
- Arrhythmias
- Valvulopathy

- Pulmonary hypertension
- Cerebrovascular events/stroke and transient ischemic attack
- Peripheral arterial thromboembolism
- Deep venous thrombosis/pulmonary embolism
- Revascularization

12.4.4. Recording of AEs and SAEs

AEs and SAE Recording:

- When an AE/SAE occurs, it is the responsibility of the investigator to review all documentation (e.g., hospital progress notes, laboratory, and diagnostics reports) relative to the event.
- The investigator will then record all relevant information regarding an AE/SAE in the CRF
- It is **not** acceptable for the investigator to send photocopies of the subject's medical records to GSK in lieu of completion of the GSK, AE/SAE CRF page.
- There may be instances when copies of medical records for certain cases are requested by GSK. In this instance, all subject identifiers, with the exception of the subject number, will be blinded on the copies of the medical records prior to submission of to GSK.
- The investigator will attempt to establish a diagnosis of the event based on signs, symptoms, and/or other clinical information. In such cases, the diagnosis will be documented as the AE/SAE and not the individual signs/symptoms.
- Subject-completed Value Evidence and Outcomes questionnaires and the collection of AE data are independent components of the study.
- Responses to each question in the Value Evidence and Outcomes questionnaire will be treated in accordance with standard scoring and statistical procedures detailed by the scale's developer.
- The use of a single question from a multidimensional health survey to designate a cause-effect relationship to an AE is inappropriate.

12.4.5. Evaluating AEs and SAEs

Assessment of Intensity

- The investigator will make an assessment of intensity for each AE and SAE reported during the study and grade each AE and SAE according to the DAIDS toxicity scales (Division of AIDS Table for Grading the Severity of Adult and Paediatric Adverse

Events, [Appendix 5](#)).

- An event is defined as ‘serious’ when it meets at least one of the pre-defined outcomes as described in the definition of an SAE.

Assessment of Causality

- The investigator is obligated to assess the relationship between study treatment and the occurrence of each AE/SAE.
- A "reasonable possibility" is meant to convey that there are facts/evidence or arguments to suggest a causal relationship, rather than a relationship cannot be ruled out.
- The investigator will use clinical judgment to determine the relationship.
- Alternative causes, such as natural history of the underlying diseases, concomitant therapy, other risk factors, and the temporal relationship of the event to the study treatment will be considered and investigated.
- The investigator will also consult the Investigator Brochure (IB) and/or Product Information, for marketed products, in the determination of his/her assessment.
- For each AE/SAE the investigator **must** document in the medical notes that he/she has reviewed the AE/SAE and has provided an assessment of causality.
- There may be situations when an SAE has occurred and the investigator has minimal information to include in the initial report to GSK. However, **it is very important that the investigator always make an assessment of causality for every event prior to the initial transmission of the SAE data to GSK.**
- The investigator may change his/her opinion of causality in light of follow-up information, amending the SAE data collection tool accordingly.
- The causality assessment is one of the criteria used when determining regulatory reporting requirements.

Follow-up of AEs and SAEs

- The investigator is obligated to perform or arrange for the conduct of supplemental measurements and/or evaluations as may be indicated or as requested by GSK to elucidate as fully as possible the nature and/or causality of the AE or SAE.
- The investigator is obligated to assist. This may include additional laboratory tests or investigations, histopathological examinations or consultation with other health care professionals.
- [If a subject dies during participation in the study or during a recognized follow-up period, the investigator will provide GSK with a copy of any post-mortem findings, including histopathology.]
- New or updated information will be recorded in the originally completed CRF.

- The investigator will submit any updated SAE data to GSK within the designated reporting time frames.

